# 2. Protocol Synopsis

	(NEWTON AF)
Study Objective(s)	To demonstrate the safety and effectiveness of the IntellaNav StablePoint Catheter and Force Sensing System with DIRECTSENSE for treatment of drug refractory, recurrent, symptomatic Paroxysmal Atrial Fibrillation (PAF).
Planned Indication(s) for Use	The IntellaNav StablePoint Catheter System, when used with a compatible Radiofrequency Controller and Irrigation Pump, is indicated for:
	Cardiac electrophysiological mapping
	Delivering diagnostic pacing stimuli
	
 
RF ablation of sustained or recurrent type I atrial flutter in patients age 18 years or older
 

	
 
Treatment of drug refractory, recurrent, symptomatic, Paroxysmal Atrial Fibrillation in patients age 18 years or older, when used with a compatible mapping system
 

	Treatment will occur according to the approved indication for use within each geography and the defined inclusion/exclusion criteria within this protocol.
Test Device and	The test devices for the study (henceforth called IntellaNav StablePoint Catheter System) include:
sizes, if applicable	
 
IntellaNav StablePoint Catheter, enabled for Force and DIRECTSENSETM
 

	IntellaNav StablePoint Catheter Cable
	IntellaNav StablePoint Connection Box     Force Computation Software Module
Control Device	There are no control devices in this study.
Study Design	The NEwTON AF study is a multi-center, global, prospective, single arm study to establish the safety and effectiveness of the IntellaNav StablePoint Catheter and Force-Sensing System in subjects with symptomatic, drug refractory, recurrent paroxysmal atrial fibrillation. The study will be conducted in North America, Europe and Asia Pacific.

Clinical Evalu	Page 5 of 129
Ci ii icai E vaiu	ation of the StablePoint Catheter and Force-Sensing System for Paroxysmal Atrial Fibrillation
	(NEWTON AF)
	A 6-month endpoint analysis is planned and will be conducted after all 299 TREATMENT subjects have completed 30 days of follow up and 183 TREATMENT subjects have completed their 6-month follow-up. If effectiveness is not demonstrated at the 6-month endpoint analysis, then it may be re-evaluated at the 12-month endpoint analysis. All subjects undergoing the index procedure with the study devices will be followed up to 12 months.
Planned Number of Subjects	A minimum of 299 subjects treated with the IntellaNav StablePoint Catheter System (TREATMENT subjects) will be enrolled in the study. Subject enrollment will stop once approximately 299 subjects are accrued.
Planned Number of Investigational Sites / Countries	Up to 50 centers in North America, Europe and Asia-Pacific may participate in this study. Approximately 5 centers in Europe and approximately 3 centers in Asia-Pacific are planned. A minimum of 50% of the total subjects (150 out of the 299 enrolled subjects) and a minimum of 50% of the sites will be selected from the U.S. No study site will be allowed to contribute more than 15% for the first 183 TREATMENT subjects (27 subjects/center) and then once 183 subjects are enrolled, no more than 15% of the remaining subject enrollment (44 subjects/center) of the total required enrollment.
Primary Safety Endpoints	Primary Safety Endpoint at 30 Days The primary safety endpoint at 30 days is defined as the safety event-free rate at 30 days post-procedure.  Primary safety events at 30 days will consist of a composite of the following serious procedure-related and/or device-related adverse events. Events will be counted through 7 days post index procedure or hospital discharge, whichever is later, unless denoted as events counting through
	Odays post index procedure.  Death  Myocardial infarction (MI)  Vagal Nerve Injury/Gastroparesis  Transient ischemic attack (TIA)  Stroke/Cerebrovascular accident (CVA)  Thromboembolism  Pericarditis  Cardiac tamponade/perforation*  Pneumothorax

# Clinical Evaluation of the StablePoint Catheter and Force-Sensing System for Paroxysmal Atrial Fibrillation

(NEWTON AF)

- Major vascular access complications
- Pulmonary edema/heart failure
- AV block\*\*
- Atrial esophageal fistula\*
- Severe pulmonary vein stenosis ≥70% reduction in the diameter of the PV or PV branch from baseline)\*

# Primary Safety Endpoint at 12 Months

The primary safety endpoint at 12 months is defined as the safety eventfree rate at 12 months post-procedure.

Primary safety events at 12 months will consist of a composite of the following serious procedure-related and/or device-related adverse

The following events will be counted through 7 days post index procedure or hospital discharge, whichever is later:

- Death
- Myocardial infarction (MI)
- Vagal Nerve Injury/Gastroparesis
- Transient ischemic attack (TIA)
- Stroke/Cerebrovascular accident (CVA)
- Thromboembolism
- Pericarditis
- Pneumothorax
- Major vascular access complications
- Pulmonary edema/heart failure
- AV block\*

The following events will be counted through 30 days post index procedure:

Cardiac tamponade/perforation

\*Atrial esophageal fistula, cardiac tamponade/perforation and severe pulmonary vein stenosis occurring up to 30 days post-index-procedure will count as primary safety endpoint events

\*\*AV block not attributable to medication effect or vasovagal reaction.

# Clinical Evaluation of the StablePoint Catheter and Force-Sensing System for Paroxysmal Atrial Fibrillation

(NEWTON AF)

And the following events will be counted through 12 months post index procedure:

- Atrial esophageal fistula
- Severe pulmonary vein stenosis ≥70% reduction in the diameter of the PV or PV branch from baseline)
- Persistent phrenic nerve palsy\*\*
- \* AV block not attributable to medication effect or vasovagal reaction.

# Primary Effectiveness Endpoints

# Primary Effectiveness Endpoint – Acute Procedural Success

The primary effectiveness endpoint of acute procedural success is defined as the achievement of electrical isolation of all PVs using the IntellaNav StablePoint Catheter only. Electrical isolation of a PV is demonstrated by entrance block after a 20-minute waiting period. If exit block testing is performed, the PV will only be considered isolated if both entrance and exit block testing was successful.

## Primary Effectiveness Endpoint at 6 Months

This primary effectiveness endpoint at 6 months is defined as the primary effectiveness event-free rate at 6 months post-procedure.

Primary effectiveness events determining a failure are defined as:

- Acute procedural failure
- Use of amiodarone post index procedure
- Use of non-study ablation catheter in the index procedure or in a repeat procedure during the blanking period
- More than one repeat procedure during the blanking period (90) days post index procedure)
- Surgical ablation of Atrial Fibrillation (AF)/Atrial Tachycardia (AT)/Atrial Flutter (AFL) post index procedure
- Documented atrial fibrillation, or new onset of atrial flutter or atrial tachycardia between 91 days and 183\* days post index procedure captured by one of the following methods:

\*\*A non-recovered phrenic nerve palsy at 12 months occurring post index procedure will count as a chronic primary endpoint. The study will collect information on phrenic nerve palsy observed before the end of the index procedure and, in case of occurrence, will track information for potential recovery during the study visits.

Clinical Eva	aluation of the StablePoint Catheter and Force-Sensing System				
for Paroxysmal A trial F ibrillation					
	(NEWTON AF)				
	
 
≥ 30 seconds in duration recording from the study specific event monitor or Holter Monitor
 
				
	
 
≥ 10 seconds 12-lead Electrocardiography (ECG)
 
				
	
 
Any of the following interventions for atrial fibrillation, or new onset of atrial flutter or atrial tachycardia between 91 days and 183* days post index procedure:
 
				
	Repeat procedure				
	Electrical and/or pharmacological cardioversion				
	Prescribed any AAD**				
	*If evaluating the primary effectiveness endpoint at 12 months, then primary effectiveness events will include events seen through 365 days post index procedure.				
	**AADs for endpoint will consist of all Class I/III, including Amiodarone, and any Class II/IV medications taken for control of atrial fibrillation (AF)/Atrial tachycardia (AT)/Atrial flutter (AFL) recurrence.				
	Primary Effectiveness Endpoint at 12 Months				
	This primary effectiveness endpoint at 12 months is defined as the primary effectiveness event-free rate at 12 months post-procedure.				
Secondary Endpoints	Secondary Endpoints include the following:				
Enapoints	
 
Secondary Safety Endpoint – SAE and AE Rates
 
Secondary Effectiveness Endpoint 1 – New or Increased Dose of AAD
 
				
	
 
Secondary Effectiveness Endpoint 2 – Single Procedure Success defined as freedom from primary effectiveness failure without a repeat procedure
 
Secondary Effectiveness Endpoint 3 – Symptomatic Recurrence: freedom from documented symptomatic AF/AT/AFL recurrence
 
				
Additional	Other additional endpoints and analysis include, but are not limited to:				
Endpoints	
 
Changes in the quality of life measures (AFEQT and EQ-5D-5L) between baseline and 12 months follow up
 
				
	
 
Total RF time for the index procedure (defined as the summation of all RF application durations)
 
				
	Total number of RF applications				
	
 
Total fluoroscopy time for the index procedure
 
				

Cli n ical E valu	nation of the StablePoint Catheter and Force-Sensing System for Paroxysmal Atrial Fibrillation
	(NEWTON AF)
	
 
Total index procedure time
 
Freedom from recurrence of individual types of atrial arrhythmias between 91 and 365 days from index procedure: 1) AF 2) AT 3) AFL
 
Freedom from cardiovascular hospitalization at 12 months
 
Quantification of parameters used during RF Application including RF power, RF duration, contact force and Local Impedance via DIRECTSENSE™ technology
 
Descriptive summaries of primary safety and effectiveness endpoints at 12 months using the data available at the time of the 6-month analysis
 
The predicted probability of success for the primary effectiveness endpoint at 12 months based off the data available at the time of the 6-month analysis.
 

Method of Assigning Subjects to Treatment	Any subject that signs the consent form, meets eligibility criteria, has the study device inserted into the body and receives ablation therapy will be assigned to the TREATMENT group.
Follow-up Schedule	Subjects will complete a pre-discharge visit, 1-month, 3-month, 6-month, and 12-month visit.
Study Duration	Enrollment is expected to be completed in approximately 12 months; therefore, the total study duration is estimated to be approximately 24 months.
Participant Duration	The study duration for each subject is expected to be approximately 12 months.
Inclusion Criteria	History of recurrent symptomatic Paroxysmal Atrial Fibrillation (PAF), defined as atrial fibrillation (AF) that terminates spontaneously or with intervention (either procedure or drug therapy) within seven days of onset. Minimum documentation includes the following:

Clinical Ev	Page 10 of 129
Ci ii icai E va	aluation of the StablePoint Catheter and Force-Sensing System for Paroxysmal Atrial Fibrillation
	(NEWTON AF)
	symptomatic AF episodes in the patient's history within the last 6 months prior to enrollment, and
	
 
any electrocardiographically documented AF episode within 12 months prior to enrollment (see Table 10-3).
 
Subjects who are eligible for an ablation procedure for PAF according to 2017 HRS expert consensus statement on catheter ablation of atrial fibrillation;
 
Subjects refractory or intolerant to at least one class I or class III antiarrhythmic medication or contraindicated to any class I or III
 

	medications; 4. Subjects who are willing and capable of providing informed consent; 5. Subjects who are willing and capable of participating in all testing
	associated with this clinical investigation at an approved clinical investigational center;  6. Subjects whose age is 18 years or above, or who are of legal age
Exclusion	Subjects will be excluded from the study if they meet any of the following criteria:
Criteria	
 
Subjects with New York Heart Association (NYHA) Class III or IV heart failure ≤ 180 days prior to enrollment
 
Left atrial diameter ≥ 5.0 cm or left atrial volume >50 ml/m²
 

	indexed based on the most recent echocardiography + 3. Left ventricular ejection fraction < 35% based on the most recent echocardiogram +
	
 
Continuous AF lasting longer than seven (7) days
 
Subjects who have undergone any previous left atrial cardiac ablation (RF, Cryo, surgical)
 

	
 
Atrial fibrillation secondary to electrolyte imbalance, thyroid disease, or reversible or non-cardiac cause
 

	
 
Subjects who have undergone any cardiac ablation or any surgery within 30 days prior to enrollment
 
Currently implanted with a pacemaker, ICD, CRT device, or an
 

	implanted arrhythmia loop recorder  9. Active systemic infection
	
 
Unstable angina or ongoing myocardial ischemia
 
Myocardial Infarction (MI) within 90 days prior to enrollment
 

# Clinical Evaluation of the StablePoint Catheter and Force-Sensing System for Paroxysmal Atrial Fibrillation

# (NEWTON AF)

- Evidence of myxoma, left atrial thrombus or intracardiac mural thrombus++
- Previous cardiac surgery (i.e. ventriculotomy, atriotomy, CABG, PTCA, PCI, coronary stenting procedures) ≤ 90 days prior to enrollment.
- Severe valvular disease, including mechanical prosthetic mitral or tricuspid heart valves (patients with successful mitral valve repair allowed – annular ring constitutes repair);
- Any prior history of documented cerebral infarct, TIA or systemic embolism [excluding a post-operative deep vein thrombosis (DVT)] ≤180 days prior to enrollment
- Moderate or severe mitral stenosis (severity assessed on the most recent TTE ≤180 days prior to enrollment. Defined as pulmonary artery systolic pressure >30 mmHg)
- Presence of left atrial appendage closure device
- Interatrial baffle, closure device, patch, or patent foramen ovale (PFO) occluder
- Subjects who, in the judgment of the investigator, have a life expectancy of less than two (2) years
- Women of childbearing potential who are, or plan to become, pregnant during the time of the study (method of assessment upon investigator's discretion)
- Amiodarone use within 60 days prior to enrollment
- Any carotid stenting or endarterectomy
- Stage 3B renal disease or higher (estimated glomerular filtration rate, eGFR <45 mL/min)

- Known coagulopathy disorder (e.g. von Willebrand's disease, hemophilia)
- 25. Any known contraindication to an AF ablation
- Any known contraindication for anticoagulation (e.g. patients unable to receive heparin or an acceptable alternative to achieve adequate anticoagulation)
- 27. Vena cava embolic protection filter devices and/or known femoral thrombus that prevents catheter insertion from the femoral approach
- 28. Known sensitivity to contrast media (if needed during the procedure) that cannot be controlled with pre-medication
- 29. Rheumatic Heart Disease
- Presence of intramural thrombus, tumor or other abnormality that precludes vascular access, or manipulation of the catheter

# Clinical Evaluation of the StablePoint Catheter and Force-Sensing System for Paroxysmal Atrial Fibrillation

(NEWTON AF)

- 31. Subjects unable or unwilling to complete follow-up visits and examinations for the duration of the clinical study
- 32. Subjects who are currently enrolled in another investigational study or registry that would directly interfere with the current study, except when the subject is participating in a mandatory governmental registry, or a purely observational registry with no associated treatments; each instance must be brought to the attention of the sponsor to determine eligibility.

†LVEF and LA diameters obtained ≤180 days prior to enrollment will be acceptable, unless a cardiac event has occurred (e.g. MI) between the date of the exam and the enrollment date. In this case, a new echocardiogram (trans-thoracic or transesophageal, or intracardiac echo) must be performed to confirm eligibility prior to performing ablation. If no recent (≤180 days prior to enrollment) echocardiogram is available at the time of the enrollment, a new echocardiogram must be performed either prior to enrolling the patient into the study or post-consent to confirm patient's eligibility prior to performing the ablation. For TTE, LA anteroposterior diameter measured by M-mode from the parasternal long-axis view will be used. If both LA diameter and volume are available and at least one of them meets the exclusion criteria, the subject is considered ineligible for the study.

\*\*The absence of thrombus must be confirmed by means of a trans-esophageal echocardiogram (TEE) within 48 hours prior to the procedure or Intracardiac Echography (ICE) during the procedure in subjects not adequately anticoagulated per Section 10.4.2. If a thrombus is observed, the subject no longer meets eligibility criteria and should be considered "Consent Ineligible".

### Statistical Methods

# Primary Statistical Hypotheses

### Hypothesis for Primary Safety Endpoint at 30 Days

- Ho: The primary safety endpoint event-free rate at 30 days post procedure < 90%
- Ha: The primary safety endpoint event-free rate at 30 days post procedure > 90%

#### Hypothesis for Primary Safety Endpoint at 12 Months

- Ho: The primary safety endpoint event-free rate at 12 months post procedure < 89%
- · Ha: The primary safety endpoint event-free rate at 12 months post procedure > 89%

Hypothesis for Primary Effectiveness Endpoint – Acute Procedural Success

# Clinical Evaluation of the StablePoint Catheter and Force-Sensing System for Paroxysmal Atrial Fibrillation

# (NEWTON AF)

- Ho: The acute procedural success rate ≤ 92%
- Ha: The acute procedural success rate > 92%

# Hypothesis for Primary Effectiveness Endpoint at 6 Months

- Ho: The 6-month primary effectiveness event-free rate ≤ 60%
- Ha: The 6-month primary effectiveness event-free rate > 60%

# Hypothesis for Primary Effectiveness Endpoint at 12 Months

- Ho: The 12-month primary effectiveness event-free rate ≤ 50%
- Ha: The 12-month primary effectiveness event-free rate > 50%

# Statistical Test Methods

## Statistical Methods for Primary Safety Endpoints

The primary safety event-free rates at 30 days and 12 months will be calculated using Kaplan-Meier methodology. Subjects who withdraw from the study without experiencing an event will be censored on the date of their last study visit. The 95% one-sided lower confidence limit of the observed primary safety event-free rate will be compared to the performance goal (90% at 30 days, and 89% at 12 months). If the lower confidence limit is greater than the performance goal, the null hypothesis will be rejected. The lower confidence limit will be calculated as the pointwise confidence limit using the log-log methodology.

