## 11.1.4.2. Sample Size

The sample size estimate was obtained using the normal approximation to the binomial distribution and verified through simulations based on Kaplan-Meier methodology. The following assumptions were used in the sample size calculation:

Assumptions	Primary Safety at 12 Months
Expected rate	94%
Performance goal	89%
Attrition (per year)	10%
Significance level (one-sided)	2.5%
Power	80%
Sample size	299

Under the hypothesis and assumptions outlined above, the required sample size for this endpoint is 299 subjects treated with the IntellaNav StablePoint Catheter. This analysis drives the overall sample size for the NEwTON AF study.

The expected rate and performance goal for the primary safety endpoint at 12 months were determined using the meta-analysis outlined in Section 11.1.1 above and accounting for a 1% rate of safety events occurring between 30 days and 12 months.

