#### 11.1.4.3. Statistical Methods

The 12-month primary safety event-free rate will be calculated using Kaplan-Meier methodology. Subjects who withdraw from the study prior to 12 months without experiencing an event will be censored on the date of their last study visit. The 97.5% onesided lower confidence limit of the observed safety event-free rate at 12 months will be compared to the performance goal of 89%. If the lower confidence limit is greater than the performance goal, the null hypothesis will be rejected. The lower confidence limit will be calculated as the pointwise confidence limit using the log-log methodology.

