#### 11.3.2.2. Control of Type I Error

Either of the primary effectiveness endpoints at 6 or 12 months must be met to achieve study success for PMA submission. Since each of these endpoints is tested at a one-sided significance level of 0.025, the family-wise type I error across both endpoints is maintained below 0.05. The primary safety endpoint at 30 days and the primary effectiveness endpoint for acute procedural success must also be met to achieve study success for PMA submission, and both endpoints will be tested at a one-sided significance level ≤0.05. Therefore, following the methodology of the Intersection-Union Test (IUT), the overall type I error across the study success for PMA submission criteria will be maintained below 0.05.

The criteria for overall study success are the same as that for study success for PMA submission, with the added conditions that the primary safety and effectiveness endpoints at 12 months must be met. Since both endpoints will be tested at a one-sided significance level of 0.025, the overall type I error across the overall study success criteria will be maintained below 0.05.

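### The synopsis tests 12-month primary safety with a 95% one-sided limit and Section 11 with a 97.5% limit, so the same data can pass one rule and fail the other

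*Combined protocol and SAP*

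**What the plan says.** The synopsis (Section 2, Statistical Methods for Primary Safety Endpoints) gives one rule for both safety endpoints: "95% one-sided lower confidence limit of the observed primary safety event-free rate will be compared to the performance goal (90% at 30 days, and 89". Here 89% is the 12-month goal. The limit is the pointwise log-log Kaplan-Meier limit, and the null is rejected if it exceeds the goal.

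Section 11 separates the two endpoints:

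- **30 days (11.1.1.2, 11.1.1.3):** 95% one-sided limit, alpha 5%, goal 90%. This agrees with the synopsis.
- **12 months (11.1.4.3):** "The 97.5% onesided lower confidence limit of the observed safety event-free rate at 12 months" is compared with 89%, again by the log-log method. This does not agree with the synopsis.
- **12-month sample size (11.1.4.2):** one-sided 2.5%, 80% power, 94% expected against 89%, 10% yearly attrition, 299 subjects. Of this calculation the plan says: "This analysis drives the overall sample size for the NEwTON AF study".
- **Type I error (11.3.2.2):** on the 12-month safety and effectiveness endpoints, "Since both endpoints will be tested at a one-sided significance level of 0.025".

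The synopsis's own sample-size table is broken in the text as read, but it also appears to show 2.5% for 12-month safety.

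**The concern.** In a single-arm trial judged against a performance goal, the confidence level of the lower limit is the decision rule. The synopsis sentence cannot be read as covering 30 days only, because it names the 12-month goal. It sets a nominal alpha of 5% for the endpoint that sizes the trial, twice the 2.5% used everywhere else for that endpoint.

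Twelve-month safety must be met in both cases of Overall Study Success (Section 6.6.2). With two thresholds in current text and no statement of precedence, a result between them could be declared a pass or a fail by citing different pages. That leaves room for a choice after the data are seen, or for a dispute with a regulator who reads the other page.

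**Working it through.** **Inputs.** Goal p0 = 0.89, expected rate p1 = 0.94, power 80%, attrition 10% per year, N = 299 (all from 11.1.4.2). Log-log limit (11.1.4.3 and synopsis). One-sided alpha 0.025 (11.1.4.2, 11.1.4.3, 11.3.2.2) or 0.05 (synopsis).

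**1. Which alpha produced 299?** Normal approximation to the binomial, the method named in 11.1.4.2:

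n = [z(1−α)·√(p0(1−p0)) + z(power)·√(p1(1−p1))]² / (p1−p0)², then divided by 0.90 for attrition.

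- α = 0.025: [(1.960 × 0.3129 + 0.842 × 0.2375) / 0.05]² = 264.5, so 265 evaluable; 265/0.9 gives 295. The plan states 299, within about 1.5%.
- α = 0.05: [(1.645 × 0.3129 + 0.842 × 0.2375) / 0.05]² = 204.2, so 205 evaluable; 205/0.9 gives 228.

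Using only the null or only the alternative variance, with 0%, 5% or 10% attrition, alpha 0.05 reaches at most 270. The trial was sized at 2.5%.

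**2. Where do the two rules disagree?** With no censoring, n subjects and d events, S = 1 − d/n and

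lower limit = S^exp{ z·√[(1−S)/(nS)] / |ln S| }.

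Worked case, d = 23 and n = 299: S = 0.9231, |ln S| = 0.0800, √[(1−S)/(nS)] = 0.0167, ratio 0.2086.

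- 95%: exponent exp(1.645 × 0.2086) = 1.409, limit 0.9231^1.409 = 89.33%, a pass.
- 97.5%: exponent exp(1.960 × 0.2086) = 1.505, limit 0.9231^1.505 = 88.65%, a fail.

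| n | events | event-free | 95% limit | 97.5% limit |
|---|---|---|---|---|
| 299 | 22 | 92.64% | 89.71% pass | 89.04% pass |
| 299 | 23 | 92.31% | 89.33% pass | 88.65% fail |
| 299 | 24 | 91.97% | 88.95% fail | 88.26% fail |
| 269 | 19 | 92.94% | 89.87% pass | 89.15% pass |
| 269 | 20 | 92.57% | 89.44% pass | 88.71% fail |
| 269 | 21 | 92.19% | 89.01% pass | 88.28% fail |
| 269 | 22 | 91.82% | 88.59% fail | 87.84% fail |

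Here 269 is 299 × 0.9. The largest passing counts are 22 against 23 at n = 299, and 19 against 21 at n = 269.

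**3. What does the choice do to power and type I error?** Exact binomial, P(X ≤ largest passing count), with event probability 0.06 for power and 0.11 for type I error:

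| n | power, 97.5% rule | power, 95% rule | type I, 97.5% rule | type I, 95% rule |
|---|---|---|---|---|
| 299 | 86.5% | 90.8% | 2.3% | 3.7% |
| 269 | 80.9% | 91.1% | 2.0% | 5.25% |

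At n = 269 and a true 94%, 91.1 − 80.9 = about 10% of trials fall between the rules; at n = 299, 90.8 − 86.5 = about 4%.

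**4. Kaplan-Meier simulation with censoring.** N = 299, 10% yearly attrition, 10,000 runs. The timing is assumed: 5% of subjects have an event in the first week and 1% between days 30 and 365; under the 89% null the split is 10% and 1%; dropout is exponential. Power is 82.9% (97.5% rule) against 92.0% (95% rule), with 9.05% of trials in the gap. Type I error is 2.0% against 3.9%. A second simulation with uniform attrition and 20,000 runs gave 82.6% against 91.5%, and 2.0% against 4.2%.

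**The case against.** The strongest reply is that the intended rule is not in real doubt. Sections 11.1.4.2, 11.1.4.3 and 11.3.2.2 all say 2.5%, the sample size follows from 2.5%, and the synopsis's own table appears to say the same. One sentence, probably the 30-day level carried over, stands alone. Section 11.4.6 also requires changes to the planned analysis to go into an approved amendment beforehand or be reported as deviations.

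The consequences are limited too:

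- Study Success for PMA Submission (6.6.1) does not use this endpoint.
- The rules disagree at only one or two event counts.
- The overall bound of 0.05 claimed in 11.3.2.2 survives, because it rests on an intersection-union argument that a 5% test also satisfies.
- Doubling applies to the nominal alpha. Actual type I error rises about 1.6-fold at n = 299 (3.7/2.3) and about 2.6-fold at n = 269 (5.25/2.0).

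Most of this stands, and it shows which text to correct. It does not remove the contradiction. Section 11.4.6 governs changes, not two conflicting rules already in the plan, and nothing in the document gives one section precedence. The plan refers to a Statistical Analysis Plan for further detail, but no separate text on this endpoint is available here, so whether it settles the level cannot be determined.

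**Conclusion.** The concern holds. The synopsis states an operative 95% rule for 12-month safety that contradicts the 97.5% rule in Section 11, and the two give opposite verdicts at 23 events with 299 uncensored subjects and at 20 or 21 events with 269. The synopsis sentence is the one in error relative to the rest of the plan, because the sample size and three parts of Section 11 rest on 2.5%. The 30-day rule is consistent throughout, so the conflict is confined to 12 months.

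The finding does not put the sample size of 299 or the stated overall 0.05 bound in question. The event-count boundaries assume no censoring among the subjects counted. The simulated power and type I figures depend also on event and dropout timing that the plan does not specify. The contradiction itself depends on neither. It should be corrected because this is a primary pass/fail threshold required for Overall Study Success.

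**What to change.** In the synopsis, under Statistical Methods for Primary Safety Endpoints, split the sentence. State a 95% one-sided lower limit (alpha 5%) against 90% for 30-day safety, and a 97.5% one-sided lower limit (alpha 2.5%) against 89% for 12-month safety. This matches 11.1.4.2, 11.1.4.3 and 11.3.2.2. Make the change before the 12-month analysis, and check that any separate Statistical Analysis Plan text carries the same levels.

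The cost is one synopsis sentence. Sample size, power, Section 11 and study conduct are unaffected.
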